9.4. Risk Window

Within each cohort, each patient will be evaluated for safety events of interest while exposed to the index therapy and accrue person-time from the cohort index date until the first occurrence of the event of interest, discontinuation of index treatment, death, loss to follow up, exit from the register or after 7 years of follow up. Interim reports will not censor the existing comparison cohorts to match the tofacitinib cohort on index date or duration of follow up. The final report will censor all patients at 7 years. Follow-up will be uniquely determined for each safety endpoint of interest.

Some outcomes of interest in this study are thought to potentially occur at a higher rate while on drug, but that increased risk subsides after the drug is discontinued (ie, serious infections, herpes zoster, CV events, gastrointestinal (GI) perforation, progressive multifocal leukoencephalopathy (PML). Those events will be evaluated over a risk window that includes time from drug initiation until 90 days after end of treatment. When a patient initiates a new therapy within the 90-day extension, the time and events during the overlapping period will be assigned to both treatments. The 90-day extension period is implemented in part to accommodate ongoing exposure to treatments with longer half-lives, and in part to ensure that any subclinical or undiagnosed illness at time of end of treatment is captured.

For non-melanoma skin cancer (NMSC) and malignancies, the manifestation of which is expected to be delayed relative to the time of exposure, the outcomes will be evaluated using two different approaches, a once exposed always at risk approach as the primary analysis and a censor at switch approach as a secondary analysis. PML rates will also be described using this approach.

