The primary analysis will assume a once exposed always at risk paradigm, as is frequently used in study of malignancy risk due to bDMARDs. 26,14,15,24 Under this approach, follow up for each cohort continues from the cohort index date until the first of a malignancy event, loss to follow up, death or end of study. Follow up for each exposure cohort continues after switching to a new drug or discontinuation of treatment. This approach maximizes follow up time and the ability to capture long latency events, ie, events that occur or are detected years after exposure. Under this approach, events will be double-counted if a patient indexed to bDMARD switches to tofacitinib and a malignancy occurs subsequent to tofacitinib

¹ The potential mechanism for increased PML risk is poorly understood. PML will be evaluated using both on drug and once-exposed always at risk approaches.

exposure. That is, the event will be assigned to both the bDMARD and the tofacitinib exposure cohorts as will the corresponding person years since index to the respective cohorts. Because tofacitinib is expected to be used as a later line therapy, switching is expected to be non-random with most tofacitinib patients having been included in the bDMARD cohort prior to initiation of tofacitinib. In such cases, the bDMARD rate will have more associated person-years and thus a relatively lower rate than the corresponding rate in the tofacitinib cohort.

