Using this primary analytic approach, if neither tofacitinib nor bDMARDs cause an increased risk of malignancy both exposure cohort rates will reflect the background rates of malignancy from the time of index to the end of the study period and the comparative effect measure will indicate no difference in rates. If tofacitinib does cause an increased rate of malignancy, which is the effect we are most interested in detecting, a relatively higher rate will be observed in the tofacitinib exposed cohort. The once exposed always at risk approach is therefore able to detect an increased rate given the non-random switching expected to occur given use of bDMARDs prior to tofacitinib and is consistent with previous studies evaluating the risk of individual biologics. Additional analyses will be conducted to evaluate potential confounders and the impact of different latency assumptions as will be described in the SAP. Sensitivity analyses will be conducted that restrict the bDMARD comparator cohort to patients who were never exposed to tofacitinib or other non-biologic advanced therapies and compare the characteristics of those bDMARD patients ever and never exposed to tofacitinib.

Secondary analyses that censor follow up time after a switch to a different treatment class will also be performed. Among patients indexed to a bDMARD cohort, follow up will begin at index and continue until the first of an event, switch to tofacitinib or other non-biologic advanced systemic therapy, loss to follow up, death, or study end date. Similarly, for tofacitinib, follow up will begin at index and continue until the first of an event, switch to a non-JAK inhibitor-based advanced systemic therapy, loss to follow up, death or study end date. While this approach eliminates the problem of double counting, it may not allow sufficient follow up time to allow for latent effects or detection and decreases the number of events included reducing the statistical power to detect a higher risk of malignancy in tofacitinib treated patients. However, under an assumption of no latency or a very short latent period as in an aggressive tumor promoter, this approach would detect an increased risk of disease on tofacitinib relative to the risk due to bDMARDs.

Of note, several studies compared a once-exposed approach to a time on drug and other approaches and found similar rates of malignancy using an on-drug and ever-exposed approach. ^{26,14,15}

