9.10. Limitations of the Research Methods

This study is designed to assess the safety of tofacitinib within the clinical practice setting utilizing RABBIT, a well-established Germany-based rheumatology register. Despite the strengths of the register, data must be evaluated in light of their limitations. For example, consistent with most observational studies, the possibility of channeling biases, endpoint misclassification, residual confounding and generalizability are of concern when comparing event rates. As a new therapy in the EU RA treatment armamentarium, it is possible that patients treated with tofacitinib will represent those with the most severe cases of disease, longer disease duration, history of multiple failed RA therapies and physical comorbidities that place patients at increased risk for AEs. Biases resulting from channeling may present as increased rates of AEs. Comparison to internal comparators may illuminate such channeling. Stratification on key indicators of disease severity, patient characteristics and past therapies can be done for contextualization in the final report. Trend analyses may be conducted to evaluate rates over time.

The RA treatment landscape has evolved over time with the introduction of new therapies, treatment recommendations, and approaches to managing AEs. The rates of AEs and their distribution among patient-types may have changed over time. Several comparators in this study are not contemporaneous to tofacitinib treated patients. Analysis will be unable to identify or control for any changes in rates due to changes in the treatment landscape.

Event misclassification is of particular concern within the observational setting due to less stringent monitoring relative to clinical trials. While RABBIT has an established system to identify and capture endpoint data, it is not feasible in such an observational study to verify all events via source documentation.

This study will follow patients for a period of 7-years of study initiation. Conclusions may not be generalizable outside of the 7 year period since initiation of therapy.

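### Protocol 9.4 gives two end rules for malignancy follow-up (7 years for everyone, or end of study), and the worked example of 9 person-years fits only the second

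*Protocol*

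**What the plan says.** The opening paragraph of Protocol 9.4 (Risk Window) ends person-time at the first event or at "discontinuation of index treatment, death, loss to follow up, exit from the register or after 7 years of follow up". It then separates interim from final reporting. On the interim side, "Interim reports will not censor the existing comparison cohorts to match the tofacitinib cohort on index date or duration of follow up". On the final side, "The final report will censor all patients at 7 years". The paragraph closes with "Follow-up will be uniquely determined for each safety endpoint of interest".

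Later in the same section, follow-up in the primary once-exposed, always-at-risk analysis of malignancy and NMSC "continues from the cohort index date until the first of a malignancy event, loss to follow up, death or end of study". The text interpreting that analysis describes the rates as running "from the time of index to the end of the study period". The secondary, censor-at-switch analysis adds a switch stop and otherwise also ends at the study end date. PML is to be described with the always-at-risk approach as well as on drug.

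In the schematic closing 9.4, the fourth row is a patient who starts a bDMARD, moves to tofacitinib, changes treatment again and then has an event. Its once-exposed contributions are 1/9 (bDMARD) and 1/6 (tofacitinib). Its censor-at-switch contributions are 0/3 and 0/3.

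Protocol 9.10 (Limitations) adds: "Conclusions may not be generalizable outside of the 7 year period since initiation of therapy".

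**The concern.** For the always-at-risk analysis, an analyst cannot both stop every patient at 7 years and follow patients to the end of the study. The two rules differ exactly for patients indexed more than 7 years before the study ends, and those are mostly bDMARD patients.

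Two things are at stake. First, 9.4 says a switcher's cancer after tofacitinib is assigned to both cohorts, and that most tofacitinib patients are expected to have been in the bDMARD cohort first. With a cap measured from each cohort's own index date, a cancer can fall outside the bDMARD window and still inside the tofacitinib window. Second, without a cap the bDMARD rate includes person-time at times since index, and so at ages, that the tofacitinib cohort cannot reach. Malignancy is a headline endpoint, and 9.4 names a tofacitinib increase as the effect of most interest.

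**Working it through.** **1. Reproducing the plan's figure.** The censor-at-switch column gives 3 years on bDMARD before the switch in row 4. The once-exposed tofacitinib column gives 6 years from tofacitinib index to the event. So bDMARD person-years = 3 + 6 = 9 with 1 event, which is the printed 1/9. The same sum gives 3 + 2 = 5 for row 1 (printed 1/5). Row 2 has no switch: 3 + 0 = 3 (printed 1/3). The schematic is internally consistent under the end-of-study rule.

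**2. The same patient under the 7-year rule.**

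| Cohort | Index to event | End-of-study rule | 7-year rule |
|---|---|---|---|
| bDMARD | 9 years | 1/9 | 0/7 (event after censoring) |
| Tofacitinib | 6 years | 1/6 | 1/6 |

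The event leaves the bDMARD rate and stays in the tofacitinib rate.

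**3. All five example rows, once-exposed columns.**

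- bDMARD, as printed: (1+1+0+1+0)/(5+3+0+9+0) = 3/17.
- bDMARD, capped: 2/15.
- Tofacitinib, either way: (1+0+1+1+1)/(2+0+6+6+7) = 4/21. Row 5 falls exactly at 7 years and is kept.
- Ratio of tofacitinib to bDMARD: (4/21)/(3/17) = 1.08 as printed, and (4/21)/(2/15) = 1.43 capped.

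These rows were built to illustrate the accounting. The ratios show which way the rule pushes and predict nothing about the study.

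**4. Can follow-up exceed 7 years?** Inputs: bDMARD enrolment after 1 January 2009 (9.2.1.3), tofacitinib fully available May 2017 (9.2, Study Population), end of data collection 14 September 2025 (section 6).

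- bDMARD: 1 January 2009 to 14 September 2025 is about 16.7 years, up to 9.7 beyond the cap.
- Tofacitinib: May 2017 to 14 September 2025 is about 8.4 years, up to 1.4 beyond the cap.

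The rules can diverge in both cohorts, and by far more in the comparator. These are calendar maxima, not expected follow-up.

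**5. Does 7 years mean time since index or calendar time?** The opening paragraph of 9.4 speaks of years of follow-up and contrasts the final report with interim reports that are not matched on duration of follow-up. Protocol 9.10 speaks of 7 years since initiation of therapy. The calendar span in section 6, 15 September 2019 to 14 September 2025, is about 6.0 years. All three favour time since index.

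**The case against.** **Endpoint-specific override.** The opening paragraph of 9.4 can be read as a default. It also stops person-time at discontinuation, which plainly does not govern the always-at-risk analysis, and it closes with "Follow-up will be uniquely determined for each safety endpoint of interest". On that reading the malignancy rule overrides the cap and the schematic is right. This is the best counter-argument. But that closing sentence directly follows an unqualified rule for all patients. The malignancy text expressly lifts the stops for discontinuation and switching, and never mentions the 7-year stop. The override may be what was meant, but it is not stated.

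**Calendar reading.** The abstract and 9.6 use 7 years for the study period, and the sentence in 9.10 just before the one quoted speaks of 7 years from study initiation. On that reading the 7-year cut and end of study coincide. The ambiguity is real, but step 5 weighs against it.

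**Size and direction.** A reader might infer a large bias. Assume uniform bDMARD index dates from 2009, complete follow-up to September 2025 apart from 0 to 10% yearly loss, and a malignancy rate rising 4 to 6% per year of follow-up. Then 20 to 44% of bDMARD person-years would lie beyond year 7, and the uncapped crude rate would be about 6 to 22% above the capped one. The protocol does not support these as estimates. Section 9.3.2 lists follow-up visits only to month 60, and 9.4 also stops person-time at exit from the register. If observation mostly ends near month 60, the share beyond year 7 could be close to zero. The loss and slope values are not in the protocol. Nor can one conclude that the uncapped rule would hide a tofacitinib excess: 9.8 plans age/sex-standardised rates and, if feasible, comparisons adjusted for age and year of treatment start, which would reduce a crude ageing effect. Section 9.4 also plans latency analyses and a sensitivity analysis in never-tofacitinib bDMARD patients.

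**The cap is not obviously right.** The always-at-risk approach was chosen to maximise follow-up and capture long-latency events, with a switcher's event assigned to both cohorts. A cap cuts against both aims. This stands, and is why the fix below leaves the choice open.

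**A later analysis plan.** The study is descriptive, comparison depends on feasibility, and the plan may modify the protocol. That lowers the severity. It does not remove the point, because the protocol fixes two incompatible rules rather than leaving a detail open.

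**Conclusion.** The contradiction holds. Protocol 9.4 censors all patients at 7 years in the final report, while its malignancy and NMSC rules, also used for always-at-risk PML, run to end of study. The schematic's 1/9 is possible only under the latter. For that patient the choice is between counting the cancer in both cohorts (1/9 and 1/6) and counting it in tofacitinib alone (0/7 and 1/6). This rests on reading 7 years as time since cohort index, the better-supported reading.

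The choice bears mainly on the comparator, where possible follow-up reaches about 16.7 years against 8.4. Its effect on the rates cannot be fixed from the protocol. It depends on how much follow-up exists after month 60, on loss, and on the age trend in rates, and standardisation or adjustment would shrink it. The documents support neither a stated percentage bias nor a claim that one rule is the correct one. Severity: should be fixed before the final analysis.

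**What to change.** Choose one rule for malignancy, NMSC and always-at-risk PML, and make 9.4 consistent with it. Either:

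- add a stop at 7 years from cohort index to both the primary and the secondary malignancy rules, change the once-exposed bDMARD cell in row 4 of the schematic from 1/9 to 0/7 (tofacitinib stays 1/6), and note the exception this makes to assigning a switcher's event to both cohorts; or
- exempt these endpoints explicitly from the 7-year censoring sentence in the opening paragraph of 9.4, and keep 1/9.

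Whichever is primary, report the other as a labelled sensitivity analysis. In either case, show rates for both cohorts over the same range of time since index (0 to 7 years), so that late person-time available only to bDMARD patients does not drive the comparison.

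The cost is a wording change in 9.4, one table cell if the cap is chosen, and one extra analysis. If the cap is primary, the main bDMARD rate also loses its late person-years, which then appear only in the sensitivity analysis. The choice is best made before results are known.

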9.3.3 Endpoints

Endpoints in RABBIT derive from physician reports of the occurrence of any AE or event of special interest. The events of interest, based on previously identified risks in the treated and untreated RA population, include:

- 1. Serious infections (excluding TB): pneumonia, other infections of the respiratory system, infections of the CNS, sepsis, bone or joint infections, OI, other infections.
- 2. TB.
- Herpes Zoster.
- 4. Cardiac disorders: heart failure, coronary artery disease, myocardial infarction, other cardiac disorders.
- 5. Hematologic disorders: bone marrow depression and hypoplastic anaemia, decreased white blood cells, platelet disorders, other blood dyscrasia.

- Disorders of the nervous system (excluding infections): stroke, central demyelination, other disorders of the CNS, disorders of the peripheral nervous system, psychiatric disorders.
- 7. Progressive multifocal leukoencephalopathy.
- 8. Allergic conditions and hypersensitivity.
- 9. Hepatic failure.
- 10. Gastrointestinal (GI) perforations.
- 11. Pregnancy.
- 12. Thromboembolic events: deep vein thrombosis (DVT) and pulmonary embolism (PE).
- 13. Operations and hospitalisations: bone and joint surgery and other joint therapeutic procedures, other operations and (major) therapeutic procedures that lead to hospitalization.
- 14. Other serious diagnoses, symptoms, and syndromes.
- 15. NMSC.
- 16. Malignancies, excluding NMSC.
- 17. All-cause Mortality.

Rates of these endpoints of interest and their 95% CI will be reported for tofacitinib exposed and comparator cohorts every six months.

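### All-cause mortality, DVT/PE, hepatic failure and other acute endpoints are censored on the day treatment stops, although the protocol's reasons for a 90-day extension apply to them too

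*Protocol*

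**What the plan says.** Protocol section 9.4 (Risk Window) sets one default and two exceptions.

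- **Default.** Person-time runs from the index date to the first of the event, "discontinuation of index treatment, death, loss to follow up, exit from the register or after 7 years of follow up".
- **90-day exception.** It covers five outcomes: "ie, serious infections, herpes zoster, CV events, gastrointestinal (GI) perforation, progressive multifocal leukoencephalopathy (PML". For these, "Those events will be evaluated over a risk window that includes time from drug initiation until 90 days after end of treatment". Two reasons are given: continuing exposure to drugs with longer half-lives, and "in part to ensure that any subclinical or undiagnosed illness at time of end of treatment is captured".
- **Long-latency exception.** Malignancies and non-melanoma skin cancer (NMSC) are analysed with "a once exposed always at risk approach as the primary analysis and a censor at switch approach as a secondary analysis". PML is also described this way.

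The section adds that follow-up is determined separately for each endpoint, but it names no further window.

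Section 9.3.3 lists 17 endpoints, with rates due every six months. Hematologic disorders, hypersensitivity, hepatic failure, "Thromboembolic events: deep vein thrombosis (DVT) and pulmonary embolism (PE" and "All-cause Mortality" are separate items. The infection item reads "Serious infections (excluding TB", and tuberculosis has its own line.

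**The concern.** Patients often stop a drug because they have fallen ill. If counting ends on the stop date, a patient who stops during a final illness and dies two weeks later adds person-time to the mortality rate but no death. The same can happen with an embolism or a liver event that is diagnosed just after the stop. The protocol recognises this problem and deals with it for five outcomes. It gives no reason for leaving the other acute endpoints on the shortest window. Mortality is one of the outcomes that section 7 says the surveillance should examine, and the rates of these other events are meant to help find new safety signals.

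**Working it through.** **Step 1: which window applies to which endpoint.**

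| Endpoint (section 9.3.3) | Window under section 9.4 |
|---|---|
| Serious infections, herpes zoster, GI perforation, CV events | Stop date + 90 days |
| PML | Stop date + 90 days; also once exposed always at risk |
| Malignancies, NMSC | Once exposed always at risk; censor at switch as secondary |
| All-cause mortality, DVT/PE, hepatic failure, hematologic disorders, hypersensitivity | In neither exception: stop date |
| Pregnancy, operations and hospitalisations, other serious diagnoses | In neither exception: stop date |
| Tuberculosis | Unclear (step 3) |

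The CV wording does not bring in DVT/PE. Section 9.8 equates CV events with MACE, and the draft MACE code list for RABBIT in Appendix 1 has no DVT or PE term.

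**Step 2: consistency for deaths.** The Appendix 1 MACE list includes fatal events and has a block of terms that count only when fatal, among them cardiac death and sudden cardiac death. Take a cardiac death 30 days after stopping. Under the 90-day window it is a MACE. Under the default the patient left the mortality analysis 30 days earlier, so it is not a death there. The report could then hold a cardiovascular death that is absent from its total deaths.

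**Step 3: tuberculosis.** Section 9.3.3 takes it out of serious infections. The background in section 7 counts it among them. Appendix 1 defines serious infections for RABBIT by the whole MedDRA infections class with no tuberculosis exclusion. Whether tuberculosis gets the 90 days depends on which text is followed.

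**Step 4: size.** The plan states no figure that depends on this window, so there is none to reproduce. Inputs:

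- s = 30% per year leaving tofacitinib (section 9.6, Table 2 assumption), used here as the stopping proportion;
- extension = 90 days (section 9.4);
- k = event rate in the 90 days after stopping divided by the on-drug rate. The documents do not give it; assumed range 0.5 to 5.

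Extension person-years per on-drug person-year, if each stop contributes the full 90 days:

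f = −ln(1 − s) × 90/365.25 = 0.3567 × 0.2464 = 0.088

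Bias of the on-drug-only rate relative to the rate with the extension: (1 + f)/(1 + kf) − 1. Share of events left uncounted: kf/(1 + kf).

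| k | Events uncounted | Bias of the rate |
|---|---|---|
| 0.5 | 4.2% | +4.2% |
| 1 | 8.1% | 0% |
| 2 | 14.9% | −7.5% |
| 3 | 20.9% | −13.9% |
| 5 | 30.5% | −24.4% |

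With s = 10%, f = 0.026 and the bias is −2.5% at k = 2 and −9.2% at k = 5.

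**The case against.** **Deferral to the SAP.** Section 9.4 says follow-up is set per endpoint, and section 9.8 leaves detailed methods to an SAP that may modify the protocol. That would answer a missing detail. Here a default is stated, the list of exceptions is closed, and rates go out every six months under that default.

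**Deliberate restriction.** The 90 days are reserved for outcomes whose raised risk is thought to subside after stopping. This carries weight for pregnancy and planned operations. It does not explain the acute medical endpoints: if their risk does not subside, they need a longer window, as malignancy has, and not a shorter one.

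**Standing of the study.** It is descriptive, and the three outcomes named first in the title all have explicit windows. That limits the consequences but does not resolve the conflict over deaths.

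Four stronger readings are tempting, and the documents do not support them:

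- *Every default endpoint has an understated rate.* Stopping the count removes person-time as well as events. The rate falls only if k > 1, and no k is given.
- *The share of events lost equals the fall in the rate.* It does not: at k = 2, 14.9% of events are lost and the rate is 7.5% lower.
- *The rule favours tofacitinib.* That needs a difference between cohorts in how stop dates are recorded. The protocol describes none, and section 9.1 says capture and follow-up are the same in all cohorts.
- *Tuberculosis events are lost.* The text contradicts itself on tuberculosis, so exclusion is one reading of it only.

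**Conclusion.** The point stands as a rule that is stated but badly fixed. All-cause mortality, DVT/PE, hepatic failure and the other acute endpoints stop counting on the stop date, against the protocol's own reasons for the extension. For deaths the rule also makes MACE and all-cause mortality inconsistent, whatever the size of the bias.

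Where illness leads to stopping, the on-treatment rate is probably too low, and this is most plausible for death. At 30% annual stopping the bias is between 0% and about −24% for k from 1 to 5, and the sign reverses below k = 1. These figures rest on an assumed k, on a switching proportion that section 9.6 takes from bDMARD use in Italy, and on a full 90 days after every stop. They show scale only and do not estimate the actual bias.

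**What to change.** In section 9.4, state a window for each of the 17 endpoints. Extend the window from index date to 90 days after end of treatment to all-cause mortality, DVT/PE, hepatic failure and the other acute medical endpoints. Pregnancy and operations need not follow, but the choice should be stated. For all-cause mortality, also report a once-exposed-always-at-risk rate, as already planned for malignancy. Reconcile section 7, section 9.3.3, section 9.4 and Appendix 1 on whether tuberculosis belongs to serious infections, so that its window is clear.

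The cost is a few sentences and no new data collection. The malignancy analysis already follows patients after discontinuation, and section 9.3.2 lists death among the events that are queried in detail. The price is some off-drug person-time, and events assigned to both treatments when a new one starts within the 90 days. Section 9.4 already accepts both for the five listed outcomes. The once-exposed mortality rate would add double counting of the kind the protocol already describes for malignancy, so it should sit beside the 90-day rate and not replace it.

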9.2.1.1. Tofacitinib Exposed Cohort Inclusion Criteria

- 1. Included in RABBIT.
- 2. Initiation of tofacitinib.

9.2.1.2. nbDMARD Cohort Inclusion Criteria

- 1. Included in RABBIT.
- 2. Enrolled after 1 January 2009.
- 3. failure of at least one DMARD and initiation of a new DMARD.
- 4. No previous exposure to bDMARD or targeted synthetic bDMARD (tsDMARD).

9.2.1.3. bDMARD Exposed Cohort Inclusion Criteria

- 1. Included in RABBIT.
- 2. Enrolled after 1 January 2009.
- 3. Initiation of bDMARD therapy.
- 4. No prior exposure to tsDMARD.

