9.6. Study Size

This active surveillance study is not intended to test a pre-specified statistical hypothesis. The size of the active surveillance population depends largely on use of tofacitinib in Germany. The targeted sample size for tofacitinib-treated patients is 500. Enrolment will not be capped at 500 but continue throughout the study period.

The bDMARD and nbDMARD populations used to contextualize event rates are well-established.

While the primary objective of the protocols is active surveillance, conducting quantitative, confounding controlled comparisons will depend on having a sufficient sample.

Table 1 and Table 2 below describe the power to detect a 2-fold difference in event rates between tofacitinib-initiators and bDMARD-initiators assuming the following:

- $\alpha = 0.05$;
- 3 different bDMARD-treated patient population sizes (reflecting roughly range of EU registers): n=11 100, n=5050, n=1650;
- 4 different tofacitinib-treated patient population sizes: n=100, n=250, n=500, n=1000;
- Estimated rates on bDMARD of 30/1000 person years (PY) (eg, serious infection), 10/1000 PY (eg, malignancy excluding NMSC), and 6/1000 PY (eg, major adverse cardiovascular events (MACE) based on previous analysis with registers (Pfizer, internal data);
- 7-year study period;
- Constant rate of accrual;
- 5% annual loss to follow up among to facitinib-treated patients.

Additionally, Table 1 assumes a 0% annual rate of switching off to facitinib, as would be true for a drug with very high persistence or for an analysis following the once exposed always at risk paradigm (see Question 8). Table 2 assumes a 30% annual rate of switching from to facitinib to a bDMARD over the study period, as previously demonstrated in the EU for bDMARDs in Italy (Eposti, 2016).²⁹

For an event with a rate of 30/1000 PY, such as serious infections, 250 patients would allow sufficient power to detect a 2-fold difference in rates between tofacitinib and bDMARD-exposed patients assuming very high persistence (Table 1), while 500 tofacitinib exposed patients would be nearly sufficient if 30% of tofacitinib treated patients switched off of tofacitinib annually.

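### The never-exposed bDMARD sensitivity analysis for malignancy selects the comparator on treatment after index, which raises its rate and attenuates the tofacitinib rate ratio

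*Protocol*

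**What the plan says.** Protocol section 9.4 (Risk Window) sets three analyses for malignancy.

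- **Primary, once exposed always at risk.** Each cohort is followed "from the cohort index date until the first of a malignancy event, loss to follow up, death or end of study". A malignancy after a switch from bDMARD to tofacitinib counts in both cohorts.
- **Sensitivity.** Analyses will "restrict the bDMARD comparator cohort to patients who were never exposed to tofacitinib or other non-biologic advanced therapies", and the characteristics of ever- and never-exposed bDMARD patients will be compared.
- **Secondary, censor at switch.** bDMARD follow-up ends at the switch to tofacitinib or another non-biologic advanced therapy. Tofacitinib follow-up ends at a switch to an advanced therapy that is not a JAK inhibitor.

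Two further statements matter. The bDMARD entry criteria (section 9.2.1.3) already require "No prior exposure to tsDMARD". Section 9.4 also expects "most tofacitinib patients having been included in the bDMARD cohort prior to initiation of tofacitinib", so switchers are an expected feature of the data. No restriction matching the never-exposed rule is placed on the tofacitinib cohort.

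**The concern.** Prior tsDMARD users cannot enter the bDMARD cohort, so for these drugs the never-exposed rule can remove a patient only for something that happens after index. Membership is then decided by the future.

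A patient must remain free of malignancy, and in follow-up, long enough to switch. Those who do are deleted together with their malignancy-free bDMARD years. Those whose malignancy came first have no further follow-up in which to switch, and stay in with their event. The comparator rate rises even if no drug has any effect.

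Section 9.4 names a raised malignancy rate on tofacitinib as the effect of most interest. A supporting analysis that pulls the ratio down by construction could wrongly weaken a signal seen in the primary analysis. Comparing the characteristics of ever- and never-exposed patients describes the selection but does not correct it.

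**Working it through.** **Inputs from the protocol**

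- Malignancy rate λ: "10/1000 PY (eg, malignancy excluding NMSC" (section 9.6).
- Effect size: "the power to detect a 2-fold difference in event rates" (section 9.6).
- Cap: "The final report will censor all patients at 7 years" (section 9.4).
- bDMARD enrolment after 1 January 2009 (9.2.1.3), tofacitinib fully available May 2017 (9.2), end of data collection 14 September 2025 (section 6).
- Loss μ: "5% annual loss to follow up among" tofacitinib-treated patients (section 9.6). Applying it to bDMARD patients is an assumption, so results are shown with μ = 0 and 0.05.

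**Assumed:** switch rate σ from bDMARD to tofacitinib or another tsDMARD of 2, 5 or 10% per year; bDMARD index dates uniform over 2009–2024; constant hazards. The 30% per year in section 9.6 is for the opposite direction.

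**Step 1. The protocol's own statement.** Section 9.4 says that if no drug raises risk, the primary comparison shows no difference. With constant rates and no channelling the model gives a primary rate ratio of 1.00, which agrees.

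**Step 2. The mechanism, one case by hand.** Take σ = 0.05, switching possible for all T = 7 years, no loss, and k = λ + σ = 0.06, so e^(−kT) = e^(−0.42) = 0.657.

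- Events before any switch, per initiator: (λ/k)(1 − e^(−kT)) = (0.01/0.06)(0.343) = 0.0572.
- Person-years when censoring at switch: (1 − e^(−kT))/k = 0.343/0.06 = 5.716. Rate: 0.0572/5.716 = 10.0 per 1000 PY.
- Person-years of never-switchers: λ[1 − e^(−kT)(1 + kT)]/k² + T·e^(−kT) = 0.186 + 4.599 = 4.785. Rate: 0.0572/4.785 = 11.9 per 1000 PY.

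The numerators are identical. The restriction only removes 5.716 − 4.785 = 0.93 malignancy-free person-years per initiator.

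**Step 3. Calendar limits.** For entry date c, let t₀ = max(0, May 2017 − c), T = min(7, September 2025 − c), S(t) = exp{−(λ+μ)t} and G(t) = exp{−σ·max(0, t − t₀)}. The never-exposed rate is ∫λSG dt divided by [∫t(λ+μ)SG dt + T·S(T)G(T)], with both summed over entry dates.

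For the primary analysis under a true doubling, switched survivors are W(t) = ∫σS(s)G(s)exp{−(2λ+μ)(t−s)}ds for s from t₀ to t. The bDMARD rate is ∫(λSG + 2λW)/∫(SG + W). The tofacitinib rate is 20 per 1000 PY.

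| Switch rate per year | Never-exposed rate per 1000 PY (μ=0; 0.05) | Null RR | True RR 2, never-exposed | True RR 2, primary | True RR 2, bDMARD censored at switch |
|---|---|---|---|---|---|
| 2% | 10.4; 10.4 | 0.96; 0.96 | 1.92; 1.92 | 1.94; 1.95 | 2.00 |
| 5% | 11.1; 11.0 | 0.90; 0.91 | 1.80; 1.81 | 1.87; 1.87 | 2.00 |
| 10% | 12.3; 12.1 | 0.81; 0.83 | 1.63; 1.65 | 1.77; 1.78 | 2.00 |

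In each row the restriction attenuates more than the double-counted primary analysis.

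**Step 4. Upper bound.** If every patient could switch throughout the 7 years (no loss), inflation would be 7, 19 and 44%. That cannot apply to the whole cohort, because early entrants had no tofacitinib to switch to.

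**Step 5. The protocol's schematic** (section 9.4, bDMARD-indexed rows). Primary: (1+1+1)/(5+3+9) = 3/17. Censor at switch: (0+1+0)/(3+3+3) = 1/9. Never exposed: 1/3. These rows are illustrations, not expected rates, but they show the deleted time.

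**The case against.** **The same section already plans a censor-at-switch analysis.** This is true, and for the bDMARD arm it is the needed rule. An inflated never-exposed rate would appear beside it and beside the primary result. That limits the harm. However, the secondary analysis also censors tofacitinib, and the protocol concedes that it may leave too little follow-up for latent effects. It does not fully replace a sound sensitivity analysis.

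**How exposure is ascertained after a malignancy is not stated.** If later tsDMARD use were recorded over the whole window regardless of malignancy, and malignancy did not change later switching, the modelled bias disappears (10.0 per 1000 PY). Both conditions are needed and the protocol states neither. The result here rests on its stated rule that follow-up ends at the first malignancy.

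**Channelling could push the other way.** With 30% of patients at two- to threefold malignancy risk and twice the switch rate (all 7 years, 5% loss), the never-exposed rate is still 11.7–12.0 at 5% switching and 14.0–14.5 at 10%. The ordering against the primary analysis is less firm: under a true doubling at 5% switching the ratios are 1.83–1.95 against 1.85–1.92.

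**Stronger readings a reader might infer.** One is that the analysis hides a tofacitinib risk. The figures show attenuation. Bringing a true ratio of 2 down to about 1 takes some 20% switching per year over all 7 years. A rough gauge is 558 projected tofacitinib patients in 24 months, or 279 a year. Against the 5,050–11,100 bDMARD patients in section 9.6, that is 2.5–5.5% a year if all came from bDMARD. RABBIT's own bDMARD count is not given, and other tsDMARDs would add to the rate. Another reading is that only event-free time is deleted, but post-switch events go too. A third is that the analysis exists to test double counting, a purpose the protocol does not state.

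**Conclusion.** The point holds as a moderate flaw in one committed sensitivity analysis. As written, the restriction conditions on treatment after index, raises the bDMARD malignancy rate and lowers the tofacitinib rate ratio.

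At assumed switching of 2, 5 and 10% per year with the calendar limits, inflation is roughly 4, 11 and 22%. Without channelling, a true ratio of 2 is read further from 2 than in the primary analysis. The size rests on the assumed switch rate, constant hazards, and exposure status being settled by the end of malignancy follow-up.

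A reader might infer that the malignancy evaluation as a whole is compromised. The document does not support that. The primary and secondary analyses do not select on the future, the study tests no prior hypothesis, and comparisons are made only if feasible.

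**What to change.** Replace the restriction in section 9.4, and carry it into the SAP. Keep every bDMARD initiator, end bDMARD follow-up at the first tofacitinib or other non-biologic advanced therapy, and keep tofacitinib follow-up once exposed always at risk. Report the result beside the existing secondary analysis. Keep the ever/never comparison of characteristics as description only.

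The change is one sentence and needs no new data. Its downsides should be stated:

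- There is less bDMARD person-time than in the primary analysis.
- Switching may be informative; censoring weights can be added.
- Late bDMARD-related cancers in switchers are counted to tofacitinib alone, a bias in the opposite direction that a lag analysis can examine.
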